6.2.9.2. Tumor Imaging

Contrast-enhanced CT (without contrast if use of contrast is contraindicated) or gadolinium-enhanced MRI of the chest, abdomen, and pelvis will be performed at screening, every 8 weeks during the study and at the EOS visit if one has not been performed within the last 8 weeks. CT is the preferred imaging modality for this study. Tumor burden will be evaluated solely based on radiographic imaging per RECIST v 1.1, with the modifications noted in Section 6.2.9.1. Chest x-ray, ultrasound, endoscopy, laparoscopy, positron-emission tomography, radionuclide scans, or tumor markers will not be considered for response assessment.

For radiographic evaluations, it is recommended that the same method of assessment and the same technique (eg, scan type, scanner, subject position, dose of contrast, injection/scan interval) should be used to characterize each identified and reported lesion at baseline and during study treatment and follow-up. Local site study team reading (investigator assessment with site radiology reading) based on RECIST 1.1 will be used to determine subject eligibility.

Scans taken as part of standard medical practice up to 28 days prior to randomization can be used for Screening as long as they are of diagnostic quality and meet all study requirements. During the treatment phase, scans may be performed at time points other than every 8 weeks as clinically indicated to assess tumor progression.

For subjects who stop study treatment in the absence of disease progression (eg, experienced unexpected toxicity), scans should continue to be collected approximately every 8 weeks until disease progression or initiation of systemic anti-tumor therapy other than the study treatment, whichever is earlier.

All relevant clinical and radiographic information required to make each assessment must be made available for source verification and submission to a central reader. CCI [REDACTED] Disease progression will be determined by the investigator or qualified designee.

Imaging should be continued at protocol-specified intervals until whichever of the following occurs first:

- Initial site-assessed disease progression is confirmed
- The start of new anti-cancer treatment
- Withdrawal of consent
- Death
- The end of the study

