8.1.3. Secondary Endpoint

The secondary endpoints of this study are:

- Progression free survival, defined as the interval from the date of randomization to the earlier of the first documentation of definitive disease progression or death from any cause.
- Overall survival, defined as the interval from date of randomization to death from any cause.

- Duration of response, defined as the interval from the date of the first response (CR or PR) is achieved to the earlier of the first documentation of definitive disease progression or death from any cause.
- Occurrence of adverse events and laboratory abnormalities during treatment.

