3.8.2. Analysis Visit Windows

Subject visits might not occur on protocol-specified days. Therefore, for the purpose of analysis, observations will be assigned to analysis windows.

The analysis windows for chemistry, hematology and vital signs are provided in [Table 1](#). The analysis windows for urinalysis, pregnancy test, ECG, and ECOG are provided in [Table 2](#). The analysis windows for Thyroid Function Tests (TSH, T3, and free T4) are provided in [Table 3](#). The analysis windows for tumor assessments are provided in [Table 4](#).

Table 1. Analysis Visit Windows for Chemistry, Hematology and Vital Signs

Analysis Visit	Study Day	Lower Limit (inclusive)	Upper Limit (inclusive)
Baseline	1	-28	1 (before 1 st dose)
Week 2	15	1 (after first dose)	21
Week 4	29	22	35
Week 6	43	36	49
Week X=8, 10, ...	7*x+1	7x-6	7*x + 7
Safety Follow-up		max (andecaliximab end date, Nivo end date) + 1	max(andecaliximab end date + 30 days, Nivo end date + 5 months)

Table 2. Analysis Visit Windows for Urinalysis, Pregnancy Test, ECG, and ECOG

Analysis Visit	Study Day	Lower Limit (inclusive)	Upper Limit (inclusive)
Baseline	1	-28	1 (before 1 st dose)
Week 4	29	1 (after first dose)	42
Week 8	57	43	70
Week 12	85	71	98
Week X=16, 20, ...	7*x+1	7x-13	7*x + 14
Safety Follow-up		max (andecaliximab end date, Nivo end date) + 1	max(andecaliximab end date + 30 days, Nivo end date + 5 months)

Note. For pregnancy test, use results from serum test for screening and results from urine test for post-screening visit.

Table 3. Analysis Visit Windows for Thyroid Function Tests (TSH, T3, free T4)

Analysis Visit	Study Day	Lower Limit (inclusive)	Upper Limit (inclusive)
Baseline	1	-28	1 (before 1 st dose)
Week 8	57	1 (after first dose)	84
Week 16	113	85	140
Week 24	169	141	196
Week 32, 40,	7*x+1	7x-27	7*x + 28
Safety Follow-up		max (andecaliximab end date, Nivo end date) + 1	max (andecaliximab end date + 30 days, Nivo end date + 5 months)

Table 4. Analysis Visit Windows for Tumor Assessments

Analysis Visit	Nominal Study Day	Lower Limit (inclusive)	Upper Limit (inclusive)
Baseline	-28	Randomization date - 60	Randomization date
Week 8	57	1	84
Week 8 confirmatory	Day of Week 8 visit + 28	Day of Week 8 visit + 28	
Week 16	113	85	140
Week 16 confirmatory	Day of Week 16 visit + 28	Day of Week 16 visit + 28	
Week 24	169	141	196
Week 24 confirmatory	Day of Week 24 visit + 28	Day of Week 24 visit + 28	
Week X=32, 40, ...	$7*x+1$	$7x-27$	$7*x + 28$

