Week X=32, 40, ... confirmatory	Day of Week 32, 40, ... visit +28	Day of Week 32, 40, ... visit +28	

Note: In the rare cases where the screening assessments are after the randomization date but prior to the first dose of study drug, the assessments will be considered as baseline.

3.8.3. Selection of Data in the Event of Multiple Records in an Analysis Visit Window

Depending on the statistical analysis method, single values may be required for each analysis window. For example, change from baseline by visit usually requires a single value, whereas a time-to-event analysis would not require 1 value per analysis window.

If multiple valid, nonmissing, measurements exist in an analysis window, records will be chosen based on the following rules if a single value is needed:

- For baseline, the last nonmissing value on or prior to the first dosing date of study drug will be selected, unless specified differently. If there are multiple records with the same time or no time recorded on the same day, the baseline value will be the average of the measurements for continuous data, or the measurement with the lowest severity (eg, normal will be selected over abnormal for safety electrocardiogram [ECG] findings) for categorical data.
- For post baseline values:
 - The record closest to the nominal day for that visit will be selected.
 - If there are 2 records that are equidistant from the nominal day, the later record will be selected.
 - If there is more than 1 record on the selected day, the average will be taken for continuous data and the worse severity will be taken for categorical data, unless otherwise specified, unless otherwise specified.

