6.1.2. Analysis for the Primary Efficacy Endpoint

The ORR endpoint will be tested at a two-sided alpha level of 0.2. The ORR will be presented with corresponding 2-sided 80% and 95% exact confidence intervals (CIs) calculated using the Clopper-Pearson method. Odds ratio will also be presented with corresponding 80% and 95% CIs be calculated using the exact CMH Chi-square test stratified by screening PD-L1 status. Subjects who do not have sufficient baseline or on-study tumor assessments to characterize response will be counted as non-responders and included in the denominator only.

In addition, the confirmed ORR, defined as the proportion of subjects with best overall response of confirmed CR/confirmed PR will also be presented as a sensitivity analysis. The same analysis methods as for ORR mentioned above will be applied for confirmed ORR.

The analysis for the ORR and confirmed ORR will be performed based on the ITT Analysis Set.

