6.2. Secondary Efficacy Endpoint

6.2.1. Progression-Free Survival

Progression free survival (PFS), defined as the interval from the date of randomization to the earlier of the first definitive PD (as defined in Section 6.2.1) or death from any cause. The first definitive PD is defined as the first radiation therapy, the first clinical PD, and the first confirmed imaging PD, whichever comes first. Pseudo-PD will not be considered as definitive PD.

Data will be censored on the date of last adequate tumor assessment for subjects (including assessments with a NE outcome):

- who do not have definitive PD or die before study discontinuation, or
- who start new anticancer therapy prior (radiation therapy excluded) to definitive PD or death, or
- who have ≥ 2 consecutive missing tumor assessments before definitive PD or death.

Subjects without any adequate baseline tumor assessment are censored on the randomization date. The adequate baseline tumor assessment is defined as the window from (randomization date - 35 days) to randomization date.

PFS in months will be calculated as $(\text{date of event/censoring} - \text{date of randomization} + 1) / 30.4375$.

Survival function of PFS is estimated using Kaplan-Meier method and compared using the log-rank test stratified by PD-L1 status at screening. PFS rates at 1, 2, 3, 6, 9, 12 months, and the median with 95% CIs will be derived using Kaplan-Meier methods by treatment arm. Kaplan-Meier curves will also be provided. In addition, hazard ratio (HR) and corresponding 95% CI will be estimated for PFS using the Cox proportional hazards regression model stratified by PD-L1 status at screening.

Follow-up time in months for PFS will be summarized as a continuous variable with descriptive statistics.

- For a subject who is censored from PFS and has discontinued from tumor assessment, duration of PFS follow-up = $(\text{Date of Censoring} - \text{randomization date} + 1) / 30.4375$
- For subjects with a definitive PFS event and censored subject with ongoing tumor assessment, duration of PFS follow-up = $(\text{Date of last tumor assessment in the database} - \text{randomization date} + 1) / 30.4375$

For subjects who have imaging examinations on various dates that are nevertheless assigned to the same nominal visit, the following rules apply for the calculation of the endpoint date:

- The response date will be the last date associated with that particular imaging time point.

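### Follow-up SAP, minor correction: PFS censors at randomization, even for deaths, when the baseline scan is outside 35 days, and OS follow-up for subjects who died is left in days

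*SAP*

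**What the plan says.** **PFS definition.** SAP 6.2.1 measures PFS from randomization to "the earlier of the first definitive PD (as defined in Section 6.2.1) or death from any cause". Protocol 8.1.3 uses the same endpoint: "the earlier of the first documentation of definitive disease progression or death from any cause".

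**Baseline rule.** SAP 6.2.1 adds: "Subjects without any adequate baseline tumor assessment are censored on the randomization date". Adequacy is a matter of timing alone: "The adequate baseline tumor assessment is defined as the window from (randomization date - 35 days) to randomization date". The sentence is unconditional. Protocol 8.3, which sets out PFS censoring, has no rule about the baseline scan. It censors a death in one situation only: after two or more successive tumor assessments that are missing or inadequate.

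**Other baseline windows.** SAP 3.8.2, Table 4, places the lower limit of the baseline visit at "Randomization date - 60" days. Its note goes further: "In the rare cases where the screening assessments are after the randomization date but prior to the first dose of study drug", the scan still counts as baseline. Protocol 6.2.9.2 sets the operational limit: "Scans taken as part of standard medical practice up to 28 days prior to randomization can be used for Screening".

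**OS follow-up.** SAP 6.2.2 announces a descriptive summary of OS follow-up time in months. The formula for subjects who left the study alive divides by 30.4375. The formula for subjects who died does not.

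**Status.** SAP sections 1 and 6 say that p-values for the updated efficacy analyses are for display only and that efficacy in the study report rests on the primary analysis, which has its own SAP.

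**The concern.** Without a usable baseline scan, progression may not be measurable, and that can justify a special rule for progression. A death needs no scan. A rule that moves a known death back to randomization removes an event that the endpoint definition counts and takes the subject out of the risk set almost at once. If several such deaths fell in one arm, that arm's PFS curve would be raised.

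The SAP also foresees the subjects concerned. Table 4 labels certain older or late scans as baseline, and section 6.2.1 then treats the same subjects as having no adequate baseline for PFS. The reason for the narrower window is not given.

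The second matter is one of units. Days and months would be pooled in a single summary labelled months.

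**Working it through.** **1. Which scans trigger the PFS rule** (subject's only pre-treatment scan; windows from SAP 6.2.1, SAP Table 4 and its note, and protocol 6.2.9.2)

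| Timing of scan | Within protocol's 28 days | Baseline in Table 4 | Adequate in SAP 6.2.1 | Death without prior progression or other censoring |
|---|---|---|---|---|
| 0 to 28 days before randomization | yes | yes | yes | event |
| 29 to 35 days before | no | yes | yes | event |
| 36 to 60 days before | no | yes | no | censored at randomization |
| After randomization, before first dose | no | yes, by the note | no | censored at randomization |
| No scan, or more than 60 days before | no | no | no | censored at randomization |

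The three pre-randomization windows are nested (28 within 35 within 60), so a scan taken to protocol never triggers the rule.

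**2. Effect on one subject.** The SAP formula is (date of event or censoring − date of randomization + 1)/30.4375.
- Censored at randomization: (0 + 1)/30.4375 = 0.03 months.
- Death on Day 90, with the randomization date as Day 1: (89 + 1)/30.4375 = 2.96 months.

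**3. Effect on one arm (assumed illustration).** Take an arm of 60, true 3-month PFS of 50% (30 events) and no other censoring. If k of the 30 events are deaths censored at randomization, the risk set falls to 60 − k while 30 subjects remain event-free, so the Kaplan-Meier estimate is 30/(60 − k).
- k = 0: 30/60 = 50.0%
- k = 1: 30/59 = 50.8%
- k = 2: 30/58 = 51.7%
- k = 3: 30/57 = 52.6%

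The shift is 0.8 to 2.6 percentage points. The binomial standard error of 50% with 60 subjects is √(0.5 × 0.5/60) = 6.5 points, so k = 3 moves the estimate by about 0.4 standard errors (2.6/6.5).

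**4. OS follow-up.** The formula for subjects who died yields days; dividing by 30.4375 gives months.
- 183 days: 183 as written, 183/30.4375 = 6.0 months
- 365 days: 365 as written, 365/30.4375 = 12.0 months
- 731 days: 731 as written, 731/30.4375 = 24.0 months

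Assumed illustration: if every subject has 365 days and half have died, the printed mean is (365 + 11.99)/2 = 188.5, labelled months, against a true 12.0.

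**The case against.** The strongest reply is that little depends on this text. The follow-up efficacy results are displays, and the study report takes efficacy from elsewhere. The affected group may be empty: measurable disease is an inclusion criterion, a subject not randomized within 28 days of screening is a screen failure, eligibility exemptions are prohibited, and Day 1 must fall within 3 days after randomization. All of this stands, and it is why the point is only a minor correction.

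A second reply is that the windows do different jobs. Table 4 assigns scans to analysis visits, 6.2.1 sets adequacy for PFS, and the protocol's 28 days is a screening limit. This also stands. The difference in days is not in itself an error, but it needs one sentence of explanation.

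A third reply is that censoring some deaths is an accepted choice. Protocol 8.3 does so after successive missing or inadequate scans, and SAP 6.2.1 does so after missing scans or new anticancer therapy. Those rules keep the subject's time up to the last adequate assessment, however, whereas the baseline rule discards all of it and has no basis in protocol 8.3. A declared change from the protocol could lie in redacted SAP text (section 6.3), so I do not say that the departure is undeclared.

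A reader might infer more in two places:
- **Negative DOR.** SAP 6.2.3 carries the PFS censoring rules into DOR, so a responder could seem to be censored before the response began. That requires the subject to count as a responder. SAP 6.1.2 says "Subjects who do not have sufficient baseline or on-study tumor assessments to characterize response will be counted as non-responders" and does not define sufficient, so the case may never arise.
- **Non-evaluable scans.** SAP 6.2.1 and protocol 8.3 describe these differently, but whether censoring dates would differ turns on the word inadequate, which the protocol does not define.

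Neither carries weight here.

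**Conclusion.** Two rules in the follow-up SAP give wrong results if followed literally, and both are minor corrections.

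The baseline rule in 6.2.1 conflicts with the PFS definition in both documents and with protocol 8.3. It reaches only subjects with no baseline scan or one outside the 35-day window. Their number is unknown and probably small. The arm-level shift of 0.8 to 2.6 points rests on the assumed 50% PFS and on 1 to 3 affected deaths, neither of which comes from the documents.

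The missing divisor in 6.2.2 is certain on the page and is most likely a drafting slip, since the companion formula and both PFS follow-up formulas divide by 30.4375.

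It would be tempting to conclude that the trial's reported PFS or OS is unreliable. The documents do not support that. Whether the primary-analysis SAP contains the same PFS rule cannot be checked, and the OS curve, log-rank test and hazard ratio do not use the follow-up formula.

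**What to change.** - **SAP 6.2.1:** count death as a PFS event whether or not the baseline scan is adequate. Align the 35-day window with the scans that Table 4 accepts as baseline, or state why PFS adequacy is narrower.
- **SAP 6.2.3:** state that randomization-date censoring does not apply to DOR. One sentence removes the ambiguity.
- **SAP 6.2.2:** divide OS follow-up by 30.4375 for all subjects.

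The cost is a few words and small programming changes, with no new data. The statistical downside is that some deaths counted this way may follow an earlier progression that could not be measured, so the event time would be later than the true one.

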6.2.2. Overall Survival

Overall survival (OS) is defined as interval from the date of randomization to death from any cause. Subjects alive are censored at the last time the subject was known alive.

The survival function of OS is estimated using Kaplan-Meier method and compared using the log-rank test stratified by PD-L1 status at screening. The median, Q1, Q3 estimate of OS and probability of survival at 3, 6, 12, 18, and 24 months from randomization will be provided along with the corresponding 95% CI. In addition, hazard ratio (HR) and corresponding 95% CI will be estimated using Cox proportional hazard regression method stratified by screening PD-L1 status.

Follow-up time in months for OS will be summarized as a continuous variable with descriptive statistics by treatment arm.

- For subjects who discontinued study without death event, duration of OS follow-up = (date of last follow-up – randomization date +1)/30.4375
- For subjects who died, duration of OS follow-up = last available date in the database – randomization date +1

The analysis of OS will be performed based on the ITT Analysis Set.

6.2.3. Duration of Response

Duration of response (DOR) is defined for subjects in the ITT analysis set who are CR/PR prior to new anti-cancer therapy (including radiation therapy) as the interval from the date of the first objective response achieved to the earlier of the first definitive disease progression or death from any cause. The first definitive disease progression is defined in Section 6.2.1. The same censoring rules as for PFS will be applied to DOR.

DOR in months = (date of event/censoring – date of first response [CR or PR] + 1) / 30.4375.

Median DOR and 95% CIs will be estimated using Kaplan-Meier methods by treatment arm. Kaplan-Meier curves will also be provided.

6.3. Exploratory Efficacy Endpoints

CCI

[REDACTED]

[REDACTED]

[REDACTED]

[REDACTED]

7. SAFETY ANALYSES

7.1. Adverse Events and Deaths

7.1.1. Adverse Event Dictionary

Clinical and laboratory adverse events (AEs) will be coded using the current version of MedDRA. System organ class (SOC) and preferred term (PT) will be provided in the AE dataset.

7.1.2. Adverse Event Severity

Adverse events are graded by the investigator as Grade 1, 2, 3, 4, or 5 according to toxicity criteria specified in the protocol. The severity grade of events for which the investigator did not record severity will be categorized as “missing” for tabular summaries and data listings. The missing category will be listed last in summary presentation.

7.1.3. Relationship of Adverse Events to Study Drug

Related AEs are those for which the investigator selected “Related” on the AE CRF to the question of “Related to Study Treatment.” Relatedness will always default to the investigator’s choice, not that of the medical monitor. Events for which the investigator did not record relationship to study drug will be considered related to study drug for summary purposes. However, by-subject data listings will show the relationship as missing.

7.1.4. Serious Adverse Events

Serious adverse events (SAEs) will be identified and captured as SAEs if the AEs met the definitions of SAEs that were specified in the study protocol as determined by the investigator. SAEs captured and stored in the clinical database will be reconciled with the SAE database from the Gilead Drug Safety and Public Health Department before data finalization.

7.1.5. Treatment-Emergent Adverse Events

7.1.5.1. Definition of Treatment-Emergent Adverse Events

Treatment-emergent adverse events (TEAEs) are defined as both of the following:

- Any AEs with an onset date on or after the study drug start date and up to 30 days after permanent discontinuation of andecaliximab or 5 months after permanent discontinuation of nivolumab
- Any AEs leading to premature discontinuation of andecaliximab or nivolumab

